#### **4.2.16.4 Primary Analysis of Exploratory Endpoint #8**

The total duration of LOS will be summarised as a continuous variable (mean, SD, median, range) by randomised treatment group in the FAS. A Wilcoxon rank-sum test by randomised treatment group will be used to calculate a two-sided p-value.

#### **4.2.16.5 Additional Analyses of the Exploratory Endpoint #8**

Not Applicable.

#### **4.2.16.6 Subgroup Analyses**

Not Applicable.

### **4.2.17 Exploratory Endpoint #9 (Frequency of K-binder use)**

*Frequency of the use of K-binders to treat HK at any time post-discharge up to 180 days in each arm.*

#### **4.2.17.1 Definition**

- Population: Full analysis set
- Endpoint: Number of participants requiring K-binders to treat HK at any time post-discharge up to 180 days in each treatment group. Number of uses of K-binders to treat HK at any time post-discharge up to 180 days
- Intercurrent event strategy: Participants who discontinue treatment, use rescue therapy for HK, experience all-cause death, have RAASI down-titration (or discontinuation), or loss to follow-up prior to 180 days post-discharge will have all K-binder use used irrespective of the intercurrent event (treatment policy strategy).
- Population level summary: Number of participants requiring K-binder use to treat HK by randomised treatment group. Mean number of uses of K-binder, by randomised treatment group. Negative binomial regression model with randomised treatment group (reference level SoC) as a main effect and including duration of time in study as an offset. The incidence rate ratio (SZC/SoC), along with 95% confidence intervals and two-sided p-values will be displayed.

#### **4.2.17.2 Derivations**

Not Applicable.

#### **4.2.17.3 Handling of Dropouts and Missing Data**

All available data on K-binder use up to 180 days post-discharge are to be used irrespective of intercurrent events, no adjustment is made for dropout. K-binders required after 180 days post-discharge will be excluded from analysis.

#### **4.2.17.4 Primary Analysis of Exploratory Endpoint #9**

A descriptive summary (Mean, SD, Median, Range) of the number of instances of K-binder use will be presented by randomised treatment group in the FAS. A negative binomial regression model will be conducted with the number of uses of K-binder as the dependent variable and randomised treatment group (reference level SoC) as the independent variable. The duration of time per participant in study is calculated until the earliest of loss to follow-up or 180 days post-discharge and will be included in the model as an offset term.. The incidence rate ratio (SZC/SoC), along with 95% CIs and two-sided p-values will be displayed.

#### **4.2.17.5 Additional Analyses of the Exploratory Endpoint #9**

Not Applicable.

#### **4.2.17.6 Subgroup Analyses**

Not Applicable.

### **4.2.18 Exploratory Endpoint #10 (K-binder use)**

*Time to first occurrence of K-binder use to treat HK post-discharge at any time post-discharge up to 180 days in each arm.*

#### **4.2.18.1 Definition**

- Population: Full analysis set
- Endpoint: Time to first use of K-binder to treat HK any time post-discharge up to 180 days inclusive.
- Intercurrent event strategy: Participants who discontinue treatment will continue to be followed up to the first use of K-binder to treat HK (treatment policy strategy). Participants who require any hospital admission or ED visits or who have RAASi down-titration (including discontinuation) will continue to be followed up to the first use of K-binder to treat HK (treatment policy strategy). Participants who die of any cause will be censored at the date of death. Participants who are lost to follow-up will be censored at the date of loss to follow-up. Participants who do not have an event by 180 days post-discharge will be administratively censored at the date of 180 days post-discharge.

- Population level summary (analysis): Kaplan-Meier plots of the survival function for the SZC and SoC treatment groups will be presented. Log-rank test for testing will be used to calculate a two-sided p-value, Cox proportional hazards ratio for estimation, with randomised treatment group (reference level SoC) as the independent variable. The HR and the two-sided 95% confidence interval will be presented. The risk difference and two-sided 95% confidence interval will be presented (as per section 4.2.2.2) at 180 days post-discharge.

#### **4.2.18.2 Derivations**

Time to first occurrence will be defined as the earliest date of (K-binder use to treat HK, date of death, loss to follow-up, date of 180 days post-discharge) – date of randomization + 1.

#### **4.2.18.3 Handling of Dropouts and Missing Data**

Participants who are lost to follow-up will be censored at the date of discontinuation as recorded on the participant's disposition form.

#### **4.2.18.4 Primary Analysis of Exploratory Endpoint #10**

The primary analysis for this exploratory endpoint will be conducted using a log-rank test by treatment group in the FAS to calculate a two-sided p-value. A Cox proportional hazards model will be used in the FAS for estimation with randomised treatment group (reference level SoC) and subject recruitment country as the independent variables.

To assess for the proportionality of hazards the log(-log(estimated survival function)) will be plotted compared to log(days) for each randomised treatment group and visually inspected to determine if the curves are approximately parallel. To assess for the impact of censoring, and the duration of follow-up, a reverse Kaplan-Meier figure will be produced where the status indicators are reversed such that the censor becomes the event and the composite event of interest as the censor. These will be presented by randomised treatment group, together with a summary of associated statistics (median time and associated 95% CIs).

#### **4.2.18.5 Additional Analyses of the Exploratory Endpoint #10**

The analysis will be repeated in the FAS using an alternative population level summary where the Cox proportional hazards model will include randomised treatment group and the following baseline variables: age (as a cubic spline), sex (female, male), participant recruitment country, presence of heart failure (yes/no), diabetes (yes/no), RAASI use (yes/no), CKD stage and baseline  $K^+$  (mild HK defined by  $5.0 < K^+ \leq 5.5$  and moderate/severe HK defined by  $5.5 < K^+ \leq 6.5$  mmol/L) as independent variables.

#### **4.2.18.6 Subgroup Analyses**

Not Applicable.

#### **4.2.19 Exploratory Endpoint #11 (Duration of K-binder use)**

*Duration of time on K-binders from initiation in the first instance of K-binder use post-discharge up to 180 days in each arm.*

##### **4.2.19.1 Definition**

- Population: Subset of full analysis set who require use of K-binders
- Endpoint: Time to discontinuation of K-binders from initiation in the first instance of K-binder use post-discharge up to 180 days in each arm.
- Intercurrent event strategy: Participants who discontinue treatment will continue to be followed up until discontinuation of K-binder (treatment policy strategy). Participants who require any hospital admission or ED visits will continue to be followed up to discontinuation of K-binder (treatment policy strategy). Participants who die of any cause will be considered to have ended K-binder use. Participants who are lost to follow-up will be considered to have ended K-binder use.
- Population level summary (analysis): Continuous summary statistics of the duration of K-binder use will be presented by randomised treatment group. A Wilcoxon rank-sum test by randomised treatment group will be used to calculate a two-sided p-value.

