Kaplan-Meier plots of the survival function for the SZC and SoC treatment groups will be presented. A log-rank test will be used to calculate a two-sided p-value. A Cox proportional hazards ratio will be used for analysis with randomised treatment group, and other covariates described in the SAP. The HR and the two-sided 95% confidence interval will be presented.

11. Duration of time on K-binders from initiation in the first instance of K-binder use post-discharge up to 180 days in each arm.

Kaplan-Meier plots of the survival function for the SZC and SoC treatment groups will be presented. A log-rank test will be used to calculate a two-sided p-value. This exploratory endpoint will be analysed using a Cox proportional hazards ratio with randomised treatment group, and other covariates described in the SAP. The HR and the two-sided 95% confidence interval will be presented.

12. Time to first occurrence of rescue therapy use to treat HK at any time post-discharge up to 180 days in each arm.

This exploratory endpoint will be analysed per exploratory endpoint #10.

13. Time to first occurrence of all-cause hospitalisations, ED visits or outpatient visits at any

time post-discharge up to 180 days in each arm.

This exploratory endpoint will be analysed per exploratory endpoint #10.

14. Rate of change in (slope) eGFR between treatment arms.

An MMRM analysis with randomised treatment group as a main effect, days post-discharge, an interaction effect between randomised treatment group and days post-discharge, as well as other covariates described in the SAP will be used to estimate the slope of eGFR by randomised treatment group.

15. Time to first occurrence of dialysis initiation at any time post-discharge up to 180 days in each arm.

This exploratory endpoint will be analysed per exploratory endpoint #10.

16. Time to first occurrence of ICU admissions at any time post-discharge up to 180 days in each arm.

This exploratory endpoint will be analysed per exploratory endpoint #10.

17. Use of RAASi at 90 and 180 days post-discharge by treatment arm.

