Exploratory	Frequency of the use of K-binder to treat HK as any time post-discharge up to 180 days in each arm.	FAS	Participants who discontinue treatment, use rescue therapy for HK, experience all-cause death, or loss to follow-up prior to 180 days post-discharge will have all K-binder use used irrespective of the intercurrent event (treatment policy strategy).	Mean number of uses of K-binder, by randomised treatment group. Negative binomial regression model with randomised treatment group as a main effect and including duration of time in study as an offset. The incidence rate ratio (SZC/SoC), along with 95% confidence intervals and two-	4.2.18

Statistical category	Endpoint	Population	Intercurrent event strategy	Population level summary (analysis)	Details in section
				sided p-values will be displayed.	
Objective 17: To evaluate the effect of continuing SZC, as part of the discharge medications, compared to SoC in reducing the duration of K-binder use.					
Exploratory	Time to discontinuation of K-binders from initiation in the first instance of K-binder use post-discharge up to 180 days in each arm.	Subset of FAS who require use of K-binders	Participants who discontinue treatment will continue to be followed up till discontinuation of K-binder (treatment policy strategy). Participants who require any hospital admission or ED visits will continue to be followed up to discontinuation of K-binder (treatment policy strategy). Participants who die of any cause will be considered to have ended K-binder use. Participants who are lost to follow-up will be considered to have ended K-binder use.	Kaplan-Meier plots of the survival function for the SZC and SoC treatment groups will be presented. Log-rank test for testing will be used to calculate a two-sided p-value, Cox proportional hazards ratio for estimation, with randomised treatment group as the independent variable. The HR and the two-sided 95% confidence interval will be presented. The risk difference and two-sided 95% confidence interval will be presented.	4.2.19
Objective 18: To evaluate the effect of continuing SZC, as part of the discharge medications, compared to SoC, in reducing the incidence of rescue therapy for HK use.					

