##### **4.2.19.2 Derivations**

Duration of K-binder use will be defined as the date of first K-binder discontinuation – date of first K-binder initiation + 1. If first K-binder discontinuation or after 180 days post-discharge then the date of first K-binder discontinuation will be administratively censored at 180 days post-discharge (date of randomisation + 180).

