##### **4.2.19.4 Primary Analysis of Exploratory Endpoint #11**

The primary analysis for this exploratory endpoint will be conducted as per section 4.2.15.4.

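### Exploratory endpoint #11 (duration of K-binder use): SAP 4.2.19 replaces the planned time-to-event analysis with a Wilcoxon test that treats use still ongoing at Day 180, or at loss to follow-up, as completed

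*SAP*

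**What the plan says.** Three places describe the analysis of this endpoint.

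- **Protocol 9.4.3.3, #11:** Kaplan-Meier plots, a log-rank p-value and a Cox model. "This exploratory endpoint will be analysed using a Cox proportional hazards ratio with randomised treatment group", with further covariates left to the SAP. It gives no rule for death or loss.
- **SAP 4.2.1 Overview, Objective 17:** the same methods. "Log-rank test for testing will be used to calculate a two-sided p-value, Cox proportional hazards ratio for estimation, with randomised treatment group". This row counts death and loss to follow-up as the end of binder use, and refers to 4.2.19 for detail.
- **SAP 4.2.19:** the endpoint in 4.2.19.1 is still a time to discontinuation, but the summary is descriptive statistics plus a rank test: "A Wilcoxon rank-sum test by randomised treatment group will be used to calculate a two-sided p-value". Section 4.2.19.4 confirms this: "The primary analysis for this exploratory endpoint will be conducted as per section 4.2.15.4", and 4.2.15.4 is the length-of-stay Wilcoxon. Section 4.2.19.2 defines duration as stop date minus start date plus 1, and says a stop beyond the window "will be administratively censored at 180 days post-discharge". On loss, 4.2.19.1 states: "Participants who are lost to follow-up will be considered to have ended K-binder use". Section 4.2.19.3 marks dropout handling as not applicable.

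Neither SAP Section 2 (changes to protocol-planned analyses) nor the SAP amendment history mentions a move from Cox to Wilcoxon here.

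**The concern.** There are two linked problems. First, the plan gives incompatible instructions for one endpoint, and the change is not declared. A programmer following the overview and one following 4.2.19 would produce different outputs.

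Second, the instruction in 4.2.19 does not fit its own endpoint. A rank-sum test takes one number per participant and has no place for a censoring indicator, so calling the Day-180 value censored has no effect on the test. Someone still taking a binder at Day 180 enters with a completed duration whose length is set by when the binder was started. Loss to follow-up is handled the same way.

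At stake is a possible misreading of an exploratory result: an arm whose binders start later could appear to need them for less time even if true time on binder is the same.

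**Working it through.** **Plan's own figure.** The documents give no figure for this endpoint. The only planning number used is the randomised total: 104 / 0.8 = 130, or 65 per arm, as in protocol 9.2.2 and the synopsis.

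**Step 1: recorded duration for a participant who never stops.** With start day *s* in days after randomisation and the stop date cut at randomisation + 180, the SAP formula gives 180 − *s* + 1 = 181 − *s*.

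| Start day | Recorded duration (days) |
|---|---|
| 7 | 174 |
| 60 | 121 |
| 120 | 61 |
| 150 | 31 |

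Someone who starts on Day 7 and stops after 60 days is recorded as 60. Someone who starts on Day 150 and never stops is recorded as 31, and so ranks as the shorter user.

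**Step 2: can start dates differ by arm?** Protocol 6.2 allows a binder in Arm B from Day 7. Protocol 6.7 allows other binders in Arm A only as rescue. SAP 4.2.19 does not say whether assigned SZC counts as a K-binder in Arm A; if it does, Arm A starts at about randomisation. Different start dates are therefore plausible, but the documents give no distribution.

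**Step 3: size, by simulation.** True time on binder was the same in both arms, so every rejection at the nominal 5% is a false positive. Assumptions:
- exponential durations;
- 13 or 26 binder users per arm (20% or 40% of 65);
- starts uniform over Days 7-60 in Arm B and Days 60-150 in Arm A;
- 20% dropout per arm (the protocol's post-randomisation figure), applied as a constant hazard over 180 days;
- 1,500 runs per scenario, so the Monte Carlo standard error at 5% is √(0.05 × 0.95 / 1500) ≈ 0.6 percentage points.

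| Mean use (days) | Cut at Day 180 | Wilcoxon, 13 / 26 per arm | Log-rank censoring Day 180 and loss, 13 / 26 per arm |
|---|---|---|---|
| 14 | about 1% | 3.1% / 5.5% | 4.5% / 6.2% |
| 60 | about 18% | 7.2% / 9.2% | 7.7% / 5.6% |
| 180 | about 49% | 37.9% / 68.4% | 4.9% / 5.0% |
| 720 | about 75% | 87.7% / 99.4% | 2.9% / 4.5% |

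With a milder separation (Arm A starts over Days 7-150), the Wilcoxon rejected in 4.5-6.2% at means of 14 and 60 days, 17.1% / 31.7% at 180 and 46.5% / 76.5% at 720.

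**Step 4: dropout alone.** With the same start dates in both arms and dropout of 10% versus 30%:
- Wilcoxon as in 4.2.19: 4.6-8.9%.
- Log-rank censoring at Day 180 but counting loss as an event, as the overview does: 5.7-14.5%.
- Log-rank censoring at Day 180 and at loss: 3.9-6.9%.

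The first problem is thus driven by the Day-180 cut combined with unequal start dates. The loss rule is a smaller, separate problem, which restoring the overview's analysis would not remove.

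**The case against.** The best defence is that this is a choice of target. The endpoint's title speaks of duration up to 180 days, days on binder within a fixed window is a legitimate utilisation measure, and the SAP caps length of stay at Day 180 in the same way (4.2.15.2). On that reading, the word censored is loose wording for a cap. Protocol 9.4.3.3 also leaves full exploratory detail to the SAP, and the overview refers the reader to 4.2.19.

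That would be a coherent plan if the documents stated it. They do not: 4.2.19.1 defines a time to discontinuation, 4.2.19.2 says censored, and the overview in the same SAP still specifies log-rank and Cox. Delegating detail to the SAP does not settle a conflict inside the SAP.

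Other parts of the defence stand. Stops before Day 180 are measured correctly. Death does end use, so counting it as an end can be a while-alive definition. The endpoint is exploratory, is not in SAP Table 5, and compares a subset formed after randomisation, so no choice of test makes it a randomised comparison.

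A reader might infer that the Wilcoxon measures start date and dropout rather than time on binder. The documents do not support that: with short courses the test kept about its nominal level even with widely separated starts, and nothing in the plan says that use will be long-term or that starts will differ by arm. A reader might also infer that censoring at loss simply restores the overview. It does not, because the overview has the same loss rule.

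**Conclusion.** The contradiction is established from the text: SAP 4.2.19 conflicts with the protocol and with the SAP's own overview, and the switch is undeclared. It is also established that the Wilcoxon in 4.2.19 ranks use ongoing at Day 180 as completed use of 181 minus the start day, and counts loss as stopping.

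The bias this produces is conditional. It is small for short courses (3-6% false positives at a mean of 14 days, 7-9% at 60). It becomes serious only if use is mostly long-term and start dates differ by arm (38-68% at a mean of 180 days when starts are well separated). These percentages rest on assumed start dates, durations and subset sizes, and show sensitivity rather than predict what the trial will find. Dropout is a minor contributor. The primary and secondary conclusions are unaffected, so this is a low-priority correction worth making because it costs little.

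**What to change.** 1. In SAP 4.2.19.1 and 4.2.19.4, replace the Wilcoxon with the Kaplan-Meier, log-rank and Cox analysis already in protocol 9.4.3.3 #11 and the SAP overview. Make K-binder discontinuation the event and censor ongoing use at Day 180. Descriptive durations can stay if the number still on binder at Day 180 is shown beside them.
2. In both 4.2.19.1 and the overview row, censor loss to follow-up instead of counting it as an event, and replace the entry in 4.2.19.3. This is a further change to the SAP, not an alignment with the overview, and should be recorded as such.
3. State the strategy for death: end of use (while alive) or a competing event.
4. Describe the result as an exploratory, non-randomised comparison in a post-randomisation subset. The same edit could say whether assigned SZC counts as a K-binder in Arm A.

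The cost is a few lines of SAP text and a change of procedure in one output, before database lock. No new data are needed, since both analyses use the same binder start and stop dates, and the dates of death and last follow-up are already required for other endpoints.

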##### **4.2.19.2 Derivations**

Duration of K-binder use will be defined as the date of first K-binder discontinuation – date of first K-binder initiation + 1. If first K-binder discontinuation or after 180 days post-discharge then the date of first K-binder discontinuation will be administratively censored at 180 days post-discharge (date of randomisation + 180).

##### **4.2.19.3 Handling of Dropouts and Missing Data**

Not Applicable

##### **4.2.19.4 Primary Analysis of Exploratory Endpoint #11**

The primary analysis for this exploratory endpoint will be conducted as per section 4.2.15.4.

##### **4.2.19.5 Additional Analyses of the Exploratory Endpoint #11**

Not Applicable.

##### **4.2.19.6 Subgroup Analyses**

Not Applicable.

#### **4.2.20 Exploratory Endpoint #12 (Rescue therapy for HK)**

*Time to first occurrence of rescue therapy use to treat HK at any time post-discharge up to 180 days in each arm.*

#### 4.2.20.1 Definition

- Population: Full analysis set
- Endpoint: Time to first use of rescue therapy to treat HK any time post-discharge up to 180 days inclusive.
- Intercurrent event strategy: Participants who discontinue treatment will continue to be followed up to the first use of rescue therapy to treat HK (treatment policy strategy). Participants who require any hospital admission or ED visits or have RAASI down-titration (including discontinuation) will continue to be followed up to the first use rescue therapy to treat HK (treatment policy strategy). Participants who die of any cause will be censored at the date of death. Participants who are lost to follow-up will be censored at the date of loss to follow-up. Participants who do not have an event by 180 days post-discharge will be administratively censored at the date of 180 days post-discharge.
- Population level summary (analysis): Kaplan-Meier plots of the survival function for the SZC and SoC treatment groups will be presented. Log-rank test for testing will be used to calculate a two-sided p-value, Cox proportional hazards ratio for estimation, with randomised treatment group (reference level SoC) as the independent variable. The HR and the two-sided 95% confidence interval will be presented. The risk difference and two-sided 95% confidence interval will be presented (as per section 4.2.2.2) at 180 days post-discharge.

#### 4.2.20.2 Derivations

Time to first occurrence will be defined as the earliest date of (rescue therapy to treat HK, date of death, loss to follow-up, date of 180 days post-discharge) – date of randomization + 1.

#### 4.2.20.3 Handling of Dropouts and Missing Data

Participants who are lost to follow-up will be censored at the date of discontinuation as recorded on the participant's disposition form.

